10.1.1. Dosing Based on Actual Potency or Nominal Strength

This section explains when the actual potency or nominal strength is to be used for dose calculations. The definitions of these terms and the types of dose calculations in this study are described below.

CONFIDENTIAL

The information contained herein may not be used, disclosed, or published without the written consent of Bioverativ Therapeutics Inc

Definitions

- The *nominal strength* is the target potency of the vial (that is, 250 IU, 500 IU, 1000 IU, or 2000 IU per vial).
- The *actual potency* is the true potency of the vial as measured by a validated potency assay. (Actual potency may vary between 80% to 125% of nominal strength.)

Calculation and Recording of Actual and Nominal Doses

Actual potency must be used for dose calculations for the following:

- ***Dosing with partial vials (Actual Potency dosing), including the dose used for the calculation of Baseline IR, the dose used for IR assessments during ITI, and any other doses where the Investigator decides to use a partial vial.*** The *actual* potency shown on the vial must be used to calculate the units of rFIXFc and the volume to inject. Actual potency dosing is required for the dose of 50 IU/kg that is used to measure Baseline IR.

Note: The instructions and worksheets provided in the DHA manual must be used to calculate the *volume for administration based on actual potency*. The actual potency shown on the vial must be used to calculate the volume for administration.

Nominal strength must be used for dose calculations for the following:

- ***Dosing with whole vials, including doses used for prophylactic treatment, treatment of bleeding episodes, surgery, and the assessment of FIX activity at interim visits.*** The *nominal* strength must be used for calculations. Whole vials will be used to achieve the target dose, rounded as described in the DHA manual. These calculations should be discussed with the parent/caregiver during regular monthly phone calls.

Note: The instructions and worksheets provided in the DHA manual must be used to calculate the *number of vials for administration based on nominal strength* (unless an equivalent alternative site-specific template is approved by the responsible CRA and the Sponsor prior to use).

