### 1) Record consolidation:

When a dose requires more than one vial and these vials are erroneously recorded in the EPD/eCRF as separate injections, albeit within a short time window, the change to consolidate these multiple records into one record is called Single Vial Consolidation (SVC). Based on the EPD set up, the programming algorithm to identify and consolidate the records is as follows:

- Identify all injection records within 60 minutes of one another where the variables (injection date/times, lot numbers, number of vials, and vials strength in nominal IU) are not exactly the same on each record. There are four scenarios:
  - Date and time of injections are not exactly same, and lot numbers, number of vials, and vials strength in nominal IU are not the same.
  - Date and time of injections are not exactly same, but lot numbers, number of vials, and vials strength in nominal IU are the same.
  - Date and time of injections are exactly same, but lot numbers, number of vials, and vials strength in nominal IU are not the same.
  - Date and time of injections are exactly same, and lot numbers, number of vials, and vials strength in nominal IU are the same, and these duplicates occurred for reasons which cannot be attributed to administrative issues as specified below.
- Consolidate injections as follows:
  - Record with earliest injection date/time retained with corresponding contextual information.
  - Combine/sum values related to the dose (e.g. lot numbers, number of vials, volume injected, nominal and actual dose) into the single retained record.

	Statistical Analysis Plan	Final v1.0
---	----------------------------------	-------------------

If injections identified with the above algorithm have distinctly different reasons (e.g., one injection is recorded as bleeding or surgery and another is recorded as prophylaxis, additional, or OTHER), then the records should NOT be consolidated. However if one reason is missing, then consolidation can be performed.

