#### **6.6. Study Drug**

Study treatment is described in Section 3.1.2. Study drug administered will be listed by patient for the FAS. This will include the reason for administration (PK assessment, episodic (treatment of a bleeding episode), prophylaxis, ITI, surgery, other), date and time of administration, dose and dosing intervals, consumption and compliance. It will also include lot number and nominal potency of the lots used.

Except for PK doses, the unit body weight dose (IU/kg) for analysis of dosing will be calculated as the total IU (nominal dose) for each injection divided by the patient’s most recent weight in kg prior to the dose of study drug.

PK doses are all 50 IU/kg at the Baseline IR Visit and the ITI regimen IR assessments, and are calculated using the actual potency of the vial (between 80 to 125% of nominal strength) and using partial vials where necessary. Therefore PK doses in the analysis are similarly calculated using the exact number of complete and partial vials, the volume and actual potency of each vial and the patient’s most recent weight.

Both types of dose are calculated as follows:

$$\text{Dose (IU/kg)} = \frac{\left( \frac{\text{Total volume administered}}{\text{Volume of vial}} \right) \times \text{Actual/Nominal Potency of Vial}}{\text{Weight (kg)}}$$

PK doses are not used for the purpose of preventing or treating bleeding and therefore the total annualized rFIXFc consumption will exclude the IU/kg amount that is used for PK doses. However, data collected over the time in which the PK dose was administered will be included in the safety analyses.

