#### 6.6.1.4. Consumption

The total annualized rFIXFc consumption (IU/kg) will be calculated for each patient using the following formula:

$$\text{Annualized consumption} = \frac{\text{Total IU/kg of rFIXFc during the efficacy period}}{\text{Total number of days during the efficacy period}} \times 365.25$$

The total amount of rFIXFc received will be the sum of the nominal IU/kg administered for each injection based on the units of rFIXFc as recorded from the patient's EPD and eCRF and his most recent weight.

Total annualized rFIXFc consumption per patient will be determined for the efficacy period (i.e., excluding the PK assessments and surgery/rehabilitation periods [major surgeries]). Total annualized consumption per patient will also be derived based on treatment regimen and overall.

Consumption is a secondary endpoint in this study. A description of how consumption will be summarized is described in Section 7.4.7.

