where the percentage of a prescribed dose is calculated as: (nominal dose taken/prescribed dose) ×100 and the “nominal dose taken” will be determined from the nominal potency labeled on the vials used by the patient for each injection of rFIXFc.

$$\text{Dose interval compliance rate} = \frac{\text{Number of doses taken within +/- 36 hours of prescribed day/time}}{\text{Total number of intervals}} \times 100$$

A patient is considered “dose compliant” or “dosing interval compliant” if his respective rate is at least 80%.

Descriptive statistics of the percentage of nominal doses taken per patient within 80%-125% range for dosing compliance as well as frequencies for the dose compliance rate (<80%, ≥80%) will be presented for the FAS. Similarly, descriptive statistics of the percentage of doses taken per patient within ±36 hours [REDACTED] of the prescribed day as well as frequencies of the dosing interval compliance rate (<80%, ≥80%) will be presented for the FAS.

	Statistical Analysis Plan	Final v1.0
---	----------------------------------	-------------------

Based on their per-patient compliance rates for dose and dosing interval (each  $<80\%$ ,  $\geq 80\%$ ), patients will be further classified into the following mutually exclusive categories for overall compliance to their prophylactic treatment as:

- Both dose and interval compliant
- Dose compliant or interval compliant (but not both)
- Neither dose nor interval compliant

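### SAP 6.6 values non-PK partial-vial doses at nominal strength, although Protocol 10.1.1 requires actual potency for them

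*SAP*

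**What the plan says.** **Protocol 10.1.1** ties the potency basis to how the vial is used. Actual potency is mandatory for partial-vial dosing, in three cases: the Baseline IR dose, the IR doses during ITI, and "any other doses where the Investigator decides to use a partial vial". Nominal strength is mandatory for "Dosing with whole vials, including doses used for prophylactic treatment, treatment of bleeding episodes, surgery, and the assessment of FIX activity at interim visits". The same section says "Actual potency may vary between 80% to 125% of nominal strength".

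**SAP 6.6** ties the basis to the purpose of the dose: "Except for PK doses, the unit body weight dose (IU/kg) for analysis of dosing will be calculated as the total IU (nominal dose"), divided by the most recent weight. The exception is narrow: "PK doses are all 50 IU/kg at the Baseline IR Visit and the ITI regimen IR assessments, and are calculated using the actual potency". One formula then serves both types of dose: volume given over vial volume, times the applicable potency, over weight.

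**Sections that use the dose.** SAP 6.6.1.4 (consumption): "The total amount of rFIXFc received will be the sum of the nominal IU/kg administered for each injection". SAP 6.6.2.2 (compliance) says that the dose taken "will be determined from the nominal potency labeled on the vials used by the patient for each injection of rFIXFc", and does not mention the volume fraction. SAP 6.6.1.3 (average prophylactic dose) and 7.4.8 (dose to resolve a bleed) state no basis of their own and so take that of 6.6.

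SAP 10, which lists the major departures from the protocol, does not mention a change of potency basis.

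**The concern.** The protocol's third case, a partial vial used for prophylaxis or a bleed, has no matching rule in the SAP. The volume drawn up is set from actual potency, and the SAP then converts that volume back to units at nominal strength. Unless the two potencies coincide, the analysed IU/kg is neither the dose aimed at nor the dose delivered.

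Two secondary endpoints are exposed: annualized consumption and dose per injection to resolve a bleed. The average prophylactic dose is exposed as well. Where a patient's partial-vial doses come from one lot, the error has the same sign each time and does not average out.

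**Working it through.** The documents state no figure for this quantity, so there is none to reproduce. The check applies the SAP 6.6 formula twice to the same injected volume.

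**Inputs**
- Relative potency r = actual/nominal, 0.80 to 1.25 (Protocol 10.1.1).
- Smallest vial 250 IU (Protocol 10.1.1); minimum weight 3.5 kg (Protocol 8.1).
- Recommended starting regimen 50 IU/kg weekly (Protocol 10.2.2.2), used only as a worked example.
- Compliance window 80% to 125% of the prescribed dose (SAP 6.6.2.2).
- Share f of the non-PK amount given from partial vials: not in the documents; assumed 10% to 100%.

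**Per-dose error.** Let v be the volume fraction, N the nominal strength and w the weight.
- Delivered dose = v × rN / w.
- Dose under SAP 6.6 = v × N / w = delivered dose / r.
- Relative error = 1/r - 1.

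| r | Error | Delivered 50 IU/kg is analysed as |
|---|---|---|
| 0.80 | +25.0% | 62.5 |
| 0.90 | +11.1% | 55.6 |
| 0.95 | +5.3% | 52.6 |
| 1.05 | -4.8% | 47.6 |
| 1.10 | -9.1% | 45.5 |
| 1.25 | -20.0% | 40.0 |

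Example: 50 IU/kg at 3.5 kg is 175 IU. From a 250 IU vial at r = 0.80 (200 IU), v = 175/200 = 0.875, and the analysis gives 0.875 × 250/3.5 = 62.5 IU/kg. At r = 1.25 (312.5 IU), v = 175/312.5 = 0.56, and the analysis gives 0.56 × 250/3.5 = 40 IU/kg.

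**Per-patient consumption.** With whole-vial doses left at nominal, as the protocol has it, the error is f × (1/r - 1).

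| Assumed f | r = 1.25 | r = 0.80 |
|---|---|---|
| 10% | -2.0% | +2.5% |
| 25% | -5.0% | +6.25% |
| 50% | -10.0% | +12.5% |
| 100% | -20.0% | +25.0% |

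In absolute terms, 50 IU/kg weekly is 50 × 365.25/7 = 2609 IU/kg per year. If every dose were a partial vial from an extreme lot, this would be reported as 2609/0.80 = 3261 or 2609/1.25 = 2087.

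**Dose compliance.** A dose measured exactly reads as 100/r percent of prescribed under the SAP 6.6 formula, which runs from 80.0% to 125.0%. With the limits included, it stays compliant. Status changes in two situations only:
- The delivered dose is itself off target. For example, 90% of prescribed at r = 1.25 reads 90/1.25 = 72%, and 110% at r = 0.80 reads 110/0.80 = 137.5%. Both are in the window when valued at actual potency and outside it as analysed.
- SAP 6.6.2.2 is applied without the volume fraction. Then 175 IU drawn from a 250 IU vial counts as 250 IU, and 250/175 = 143%.

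**The case against.** **Nominal is the protocol's own default.** Prophylaxis, bleeds and surgery are named under whole-vial dosing, and the SAP matches that. Partial vials are an Investigator option of unstated frequency. This stands. It limits the point to partial-vial doses and makes the limits in the first table per-dose extremes.

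**Two bases in one total.** Whole vials carry a similar gap, since a full vial at 80% potency delivers 80% of its analysed units. Because SAP 6.6 leaves PK doses out of consumption, consumption currently rests on nominal alone, and the fix would mix two bases. One nominal basis is a defensible convention, but the protocol sets the two bases, the SAP does not declare a departure, and a footnote deals with the mixture.

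**Limited consequence.** The primary endpoint, inhibitor development, is untouched, and the affected endpoints are descriptive. This stands and keeps the point minor.

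Three stronger readings are tempting and are not supported:
- *Infant doses in general are misstated.* At 50 IU/kg, one 250 IU vial falls within 80% to 125% for 4.0 to 6.25 kg (250/62.5 to 250/40), and 500 IU does so for 8.0 to 12.5 kg. A reader might infer that infants outside those bands must receive partial vials. But the window is a compliance criterion against the prescribed dose, not a rule for when whole vials may be used. The 50 IU/kg is only a recommended start, and rounding is set in the DHA manual, which is not available here. The arithmetic shows that partial vials are plausible, no more.
- *Correctly measured doses are classed as non-compliant.* Under the SAP 6.6 formula they read 80% to 125% and remain compliant.
- *A partial dose reads as 143% of prescribed.* This requires SAP 6.6.2.2 to override the volume fraction in SAP 6.6, and nothing says that it does. The silence warrants a cross-reference.

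**Conclusion.** Wrong as written, minor. SAP 6.6 conflicts with Protocol 10.1.1 for non-PK doses given from a partial vial, and for no others. Each such dose is misvalued by a factor of 1/r: at most +25% or -20%, and about 5% either way if potency lies within 5% of nominal. The effect on a patient's prophylactic dose, dose per bleed and annualized consumption is that error scaled by the partial-vial share. The 25% share, giving -5% to +6% at the extremes, is an illustration and not an estimate.

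The result assumes that sites set partial-vial volumes from actual potency, as the protocol requires. The extremes also assume that a patient's partial-vial doses all come from lots at the same end of the potency range. No study conclusion is shown to change.

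**What to change.** 1. In SAP 6.6, replace *Except for PK doses* with *Except for PK doses and any other dose given from a partial vial (Protocol 10.1.1)*. Value those doses as volume fraction × actual potency over weight, using the formula already there. Keep nominal strength for whole vials.
2. Carry that value into 6.6.1.3, 6.6.1.4, 7.4.8 and 6.6.2.2, and amend the nominal-only wording in 6.6.1.4 and 6.6.2.2.
3. In 6.6.2.2, refer to the SAP 6.6 formula so that the volume fraction clearly applies.
4. Footnote the two potency bases in the affected tables and report the number of partial-vial doses, which shows how far the issue reaches.

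The cost is a few lines of SAP text, one programming branch and a footnote. The inputs appear to exist: the record-consolidation rule in SAP 5.6 reads "Combine/sum values related to the dose (e.g. lot numbers, number of vials, volume injected, nominal and actual dose) into the single retained record". Programming should confirm that volume and actual potency are filled in for home injections as well as clinic ones. The downside is that some totals will combine two potency bases, which the footnote discloses.

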### 6.6.1. Exposure

#### 6.6.1.1. Number of Injections and Exposure Days to rFIXFc

For any patient, the total number of days of exposure to rFIXFc will be accumulated from the time of their first on-study injection of rFIXFc. An ED is a 24-hour period in which one or more rFIXFc injections are given. The 24-hour window starts from the first injection on study and then for subsequent injections, it starts from an injection taken after/outside of a previously identified ED.

The total number of EDs on rFIXFc for each patient will be summarized categorically (<5, 5-<10, 10-<20, 20-<50, 50-<75, 75-<100 and >=100) and with descriptive statistics for the Safety Analysis Set.

The total number of injections per patient will be summarized overall and by reason for injection (prophylactic regimen, ITI regimen, spontaneous bleed, traumatic bleed, follow-up injection, surgical and other) using descriptive statistics for the Safety Analysis Set.

These tables will be presented by treatment regimen as described in Section 5.1.1.

The total number of injections and EDs will also be summarized by EPD entry compliance (see Section 6.6.2.3), <80% and >=80%, where >=80% is considered compliant.

#### 6.6.1.2. Duration of rFIXFc Dosing

For any patient, the duration of rFIXFc dosing for a given treatment group (episodic, prophylactic, and ITI) will be calculated from the start date/time of the starting regimen to the end date/time of the last regimen in that treatment group, as defined in Sections 5.3.1 and 5.3.2. The duration of overall rFIXFc dosing will be calculated from the date/time of the first rFIXFc dose, to the end date/time of the last treatment regimen in the study. Any interruptions to dosing will not be accounted for when calculating this duration.

The number and percentage of patients whose duration of dosing was at least 13, 26, 39, 52, 65, 78, 91, 104, 117 and 130 weeks (2.5 years) will be summarized based on the integer part of the calculated week nominal for the Safety Analysis Set.

Duration of rFIXFc dosing (weeks) will also be summarized using descriptive statistics for the Safety Analysis Set. Weeks will be represented in the descriptive statistics as if these were data collected with 1 decimal place.

These tables will be presented by treatment regimen as described in Section 5.1.1.

Duration of rFIXFc dosing will also be summarized by EPD entry compliance (see Section 6.6.2.3), <80% and >=80%, where >=80% is considered compliant.

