#### **5.3.4. Duration of a Treatment Regimen**

The duration of a given treatment regimen is the time period from the start of the treatment regimen to the end of that treatment regimen. The duration will stop and start for each treatment regimen change. If a patient is treated in a given treatment regimen more than once, the total durations in the same treatment regimen will be added together. For example, if a patient is treated with the prophylactic regimen and then undergoes surgery and then goes back to the prophylactic regimen, then his total duration in the prophylactic regimen will be the sum of the two durations in the prophylactic regimen. Further details will be provided for individual analysis where needed.

The total duration of time allocated to each treatment regimen will be calculated in minutes and converted to days as the number of minutes divided by 1440.

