##### **5.4.2.1. Adjustments Due to Surgical/Rehabilitation Periods**

For analysis purposes, the efficacy period for a given treatment regimen will be adjusted for all surgical/rehabilitation periods (major and minor). The start and end of the efficacy period for a given treatment regimen are adjusted as follows:

	Statistical Analysis Plan	Final v1.0
---	----------------------------------	-------------------

- For patients on a prophylactic regimen before the start of a surgical/rehabilitation period, the efficacy period for the prophylactic regimen continues up to the last dose (for prophylaxis or bleeding) before the start of the surgical/rehabilitation period.
- For patients on the episodic regimen before the start of a surgical/rehabilitation period, the efficacy period for the episodic regimen continues up to 1 minute before the start of a surgical/rehabilitation period.
- For patients on a prophylactic regimen following the end of a surgical/rehabilitation period, the efficacy period for the prophylactic regimen starts or re-starts at the first prophylactic dose following the end of the surgical/rehabilitation period.
- For patients on the episodic regimen following the end of a surgical/rehabilitation period, the efficacy period for the episodic regimen starts or re-starts at 00:01 on the day following the end of the surgical/ rehabilitation period.

Start and end dates/times for the efficacy period for given treatment regimens and treatment regimen changes will be adjusted for each surgery (major or minor) as necessary.

For patients on a prophylactic regimen before the start of a surgical/rehabilitation period, the interval of time between the last dose before the surgical/rehabilitation period and the start of the surgical/rehabilitation period will not be attributed to the efficacy period for the prophylactic regimen. By definition, there should not be any treated bleeding episodes in this interval of time.

For patients on a prophylactic regimen following the end of a surgical/rehabilitation period, bleeding episodes that occur after discharge from a rehabilitation facility but before the next prophylactic dose will be attributed to the surgical/rehabilitation period and hence not counted towards the annualized bleeding rate (ABR).

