#### **5.4.2.2. Adjustments Due to Large Injection Intervals**

For analysis purposes, the efficacy period will also be adjusted to account for large intervals between injections resulting from missing data. A large interval is defined as >28 days between any 2 adjacent rFIXFc injections within a prophylactic treatment regimen and any such intervals will be removed from the efficacy period. The efficacy period prior to each such interval will end at the time of the first injection of this interval and restart (or start if it is the first interval of a treatment regimen) at the time of the second injection of this interval. The efficacy period will be adjusted for each identified interval that is not within a surgical/rehabilitation period. This algorithm applies only to prophylactic regimens and no adjustment for large injection intervals will be made for episodic treatment regimens.

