**7.4.3. Annualized Number of Bleeding Episodes per Patient (ABR)**

The per-patient annualized number of bleeding episodes, hereafter referred to as the annualized bleeding rate (ABR), will be calculated for each patient using the following formula:

$$ABR = \frac{\text{Number of bleeding episodes during the efficacy period}}{\text{Total number of days during the efficacy period}} \times 365.25$$

The ABR will be summarized using descriptive and categorical (e.g. 0, >0-5, >5-10, >10-15, etc.) statistics for the FAS. All types of bleeding episodes (spontaneous, traumatic, and type unknown) will be included in determining the annualized number.

These tables will be presented by treatment regimen as described in Section 5.1.1.

This analysis will also be presented by the following subgroups:

- Patients with at least 50 EDs to rFIXFc within a treatment regimen
- Patients with at least 26 weeks of rFIXFc dosing within a treatment regimen
- History of bleeding (estimated frequency of bleeds in prior 3 months: 0, 1-2, 3-5 and >5)
- Patients with no major protocol deviations potentially impacting efficacy (see Section 6.5)

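### Two SAP rules for time on a regimen conflict, the 26-week ABR subgroup names neither, and neither drops the long gaps removed from the ABR denominator

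*SAP*

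**What the plan says.** SAP Section 6.6.1.2 defines duration of dosing separately for the episodic, prophylactic and ITI groups. For each, it "will be calculated from the start date/time of the starting regimen to the end date/time of the last regimen in that treatment group". It takes its dates from Sections 5.3.1 and 5.3.2, which give only the start of the first regimen and the end of the last. It then defines overall duration and adds: "Any interruptions to dosing will not be accounted for when calculating this duration".

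SAP Section 5.3.4 defines the duration of a regimen differently. "The duration will stop and start for each treatment regimen change", and "If a patient is treated in a given treatment regimen more than once, the total durations in the same treatment regimen will be added together". Its own example is prophylaxis, then surgery, then prophylaxis, with the two prophylaxis stretches summed. Sections 5.1.1 and 5.3 likewise tie by-regimen summaries to time spent on that regimen.

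SAP Section 7.4.3 lists this ABR subgroup: "Patients with at least 26 weeks of rFIXFc dosing within a treatment regimen". It gives no cross-reference for the 26 weeks. The ABR itself divides by "Total number of days during the efficacy period". Under Section 5.4.2 the efficacy period starts from the Section 5.3.4 duration. Section 5.4.2.1 then takes out surgical and rehabilitation periods, major and minor, and Section 5.4.2.2 takes out long prophylaxis gaps: "A large interval is defined as >28 days between any 2 adjacent rFIXFc injections within a prophylactic treatment regimen".

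**The concern.** The by-regimen duration in Section 6.6.1.2 is a first-to-last span, while Section 5.3.4 adds up stints. After a switch back or an operation, the span overstates time on the regimen. After a switch back, the duration table also counts the same weeks under two regimens.

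The subgroup in Section 7.4.3 inherits the problem because it does not say which clock applies. Two programmers could build different subgroups from the same SAP. If the span is used, a child can qualify on time spent on another regimen or in surgery, although the ABR reported for that child rests on fewer than 26 weeks.

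A second mismatch does not depend on which clock is chosen. Prophylaxis gaps over 28 days are cut from the ABR denominator but are subtracted by neither duration rule, so they still help a child reach 26 weeks. Short follow-up makes an ABR unstable, and with about 30 children enrolled one such value can move a subgroup mean or maximum.

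**Working it through.** The documents give no count or ABR for this subgroup, so there is no figure to reproduce. The check applies the three clocks to hypothetical prophylaxis histories. These are assumptions, not trial data. Phases are laid end to end, ignoring the short trims around individual doses.

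**Inputs**
- Span: SAP 6.6.1.2.
- Sum of stints: SAP 5.3.4.
- Efficacy period: SAP 5.4.2, with surgery removed (5.4.2.1) and prophylaxis gaps over 28 days removed (5.4.2.2).
- ABR = bleeds / efficacy-period days × 365.25: SAP 7.4.3.
- Cut: 26 weeks × 7 = 182 days.

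**Prophylaxis weeks by each clock (P = prophylaxis, E = episodic)**

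| History in weeks | Span | Sum | Efficacy period | Reaches 26 by span / sum / efficacy |
|---|---|---|---|---|
| E 20, P 26 | 26 | 26 | 26 | yes / yes / yes |
| P 8, E 20, P 8 | 8+20+8 = 36 | 8+8 = 16 | 16 | yes / no / no |
| P 20, surgery 4, P 3 | 20+4+3 = 27 | 20+3 = 23 | 23 | yes / no / no |
| P 12, gap 5, P 10 | 12+5+10 = 27 | 27 | 12+10 = 22 | yes / yes / no |
| P 8, gap 12, P 7 | 8+12+7 = 27 | 27 | 8+7 = 15 | yes / yes / no |

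**Reading the rows**
- One-way path (row 1): all clocks agree.
- Switch back (row 2): the span is 36/16 = 2.25 times the sum. The duration table would show 36 weeks of prophylaxis and 20 of episodic treatment, 56 in all, for a child followed for 36. The 20 episodic weeks appear twice.
- Surgery (row 3): the span admits the child and the sum does not.
- Long gaps (rows 4 and 5): span and sum both admit the child. Choosing between 6.6.1.2 and 5.3.4 makes no difference here.

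**What one bleed is worth**
- 26 evaluable weeks: 365.25/182 = 2.01
- 23 weeks: 365.25/161 = 2.27
- 22 weeks: 365.25/154 = 2.37
- 16 weeks: 365.25/112 = 3.26
- 15 weeks: 365.25/105 = 3.48

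A cut at 182 efficacy-period days excludes all four interrupted histories and keeps row 1. A cut on the 5.3.4 sum excludes only rows 2 and 3.

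**The case against.** The best defence is that the SAP never ties the subgroup to Section 6.6.1.2. The reference to dosing and the 26-week category resemble that section, but the restriction to time within a regimen is at least as close to Section 5.3.4. If 5.3.4 governs, the switch-back and surgery children are correctly left out. This stands: it turns a definite error into an unresolved choice. It does not help with long gaps, which 5.3.4 leaves in.

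It can also be said that the two sections serve different purposes. Section 5.3.4 feeds the efficacy period and allows further detail for individual analyses, while 6.6.1.2 describes an exposure table. The sentence on interruptions follows the one on overall duration and may apply only to that. Both points are fair, but the span wording for each treatment group stands without that sentence, and it still departs from the time-on-regimen principle in Sections 5.1.1 and 5.3.

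Finally, the affected histories are not the expected ones. The protocol describes an optional episodic phase before prophylaxis, and on that path no other-regimen time is added. A child who reaches 50 EDs mainly on weekly prophylaxis has about 49 weeks (50 doses, 49 intervals, assuming one ED per week), far above the cut. This stands and limits the reach. The histories nevertheless remain possible: SAP Section 5.3.3 provides for a switch from prophylaxis to episodic treatment, surgery is allowed, Section 5.4.2.2 plans for long gaps, and end of study can cut follow-up short.

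A reader might infer that children with well under 26 evaluable weeks will be in this subgroup, or that the trial's ABR results are distorted. The documents support neither. Entry is a possibility that depends on the clock chosen and on individual histories.

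**Conclusion.** The point holds as an inconsistency and a gap in definition, of low priority. By-regimen duration has two conflicting rules, and Section 7.4.3 does not choose between them. If the span is used, a child with a switch back or surgery can enter the 26-week subgroup on fewer than 26 evaluable weeks. Whichever rule is used, a child with a deleted prophylaxis gap can do so.

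In the illustrations, children admitted by at least one rule have 15 to 23 evaluable weeks, and one bleed is worth an ABR of 2.27 to 3.48, against 2.01 at exactly 26 weeks. These sizes come from assumed histories, and the number of such children is unknown. Membership is wrong only where the duration used reaches 26 weeks and the evaluable time does not.

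The main ABR is unaffected because it already divides by efficacy-period days. No hypothesis is tested, and the SAP's list of tables names no separate table for this subgroup. The SAP gives no rationale for the 26-week cut. That it is meant to select children with enough follow-up for a stable rate is a reasonable assumption, not a stated purpose.

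**What to change.** In SAP Section 7.4.3, define the subgroup as patients with at least 182 efficacy-period days within the regimen, the same clock as the ABR denominator. This settles the switch-back, surgery and long-gap cases together.

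In SAP Section 6.6.1.2, use the summed duration of Section 5.3.4, with the change times of Section 5.3.3, for the by-regimen columns. Keep the uninterrupted span for overall duration only, and say that the sentence on interruptions refers to that.

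The cost is SAP wording: the SAP already defines both quantities. The subgroup may be slightly smaller.
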